1. SUMMARY

SPONSOR	Groupe Hospitalier La Rochelle Ré Aunis [name]
STUDY DIRECTOR	[name]
TITLE	Epidemiological, retrospective, multicenter study on the clinical-epidemiological characteristics and therapeutic management of non-cholera Vibrio infections (INFECTIVE).
CONTEXT	Vibrios are gram-negative, ubiquitous bacteria of the marine flora and are found particularly in warm waters. For example, the incidence is high in Florida and Vibrio infections are now reportable in the United States. Different species of Vibrio are described. We distinguish between choleric vibrios belonging to serogroups O1 and O139, responsible for cholera epidemics, and non-choleric vibrios. Our study will focus on non-epidemic vibrios. Vibrio infections develop by eating contaminated raw seafood or by exposure of a wound to the marine environment. They occur mainly during the hot summer months. This is explained on the one hand by a higher water temperature and on the other hand by an increased use of the beaches. With global warming, it is possible that Vibrio infections may increase in number and location.
OBJECTIVES	The purpose of this study is to identify the epidemiological and clinical characteristics of patients diagnosed with non-cholera Vibrio infection in Western France from 2000 to 2019. The different clinical forms will be described according to the different environmental and meteorological contexts.
DESIGN	Data-driven, retrospective, multi-center study
INCLUSION CRITERIA	- cases of non-epidemic vibriosis
EXCLUSION CRITERIA	- cases of infection with Vibrio cholerae O1 and O139
OUTCOME MEASURES	Socio-demographic, clinical and therapeutic criteria.
SAMPLE SIZE	Estimation entre 50 et 60 patients
STATISTICAL ANALYSIS	The data will be analyzed in a descriptive manner, and will be described by mean, standard deviation and median for continuous variables and by percentages for categorical variables.

2. SCIENTIFIC JUSTIFICATION AND GENERAL DESCRIPTION

2.1. CURRENT STATE OF KNOWLEDGE

Vibrios are gram-negative, ubiquitous bacteria of the marine flora and are found particularly in warm waters. For example, the incidence is high in Florida and Vibrio infections are now reportable in the United States. [1].

Different species of Vibrio are described. We distinguish between choleric vibrios belonging to serogroups O1 and O139, responsible for cholera epidemics, and non-choleric vibrios. Our study will focus on non-epidemic vibrios. Among the non-epidemic vibrios, the predominant species are *Vibrio vulnificus*, *Vibrio parahaemolyticus*, *Vibrio algolyticus* and non-O1/O139 *Vibrio cholerae*.

Vibrio infections develop by eating contaminated raw seafood - especially oysters - or by exposure of a wound to the marine environment. [2]. They occur mainly during the hot summer months. This can be explained on the one hand by a higher water temperature and on the other hand by an increased use of the beaches [3]. With global warming, it is possible that Vibrio infections may increase in number and location.

Vibrio infections are rare but can be very severe or even fatal. They present themselves in the form of gastroenteritis, severe dermohypodermatitis or necrotizing fasciitis and can lead to septic shock.

They are more common in patients with multiple co-morbidities including liver disease and heart failure [4].

Due to their rarity, Vibrio infections are very little known and therefore probably under-diagnosed. A delay in the therapeutic management with, in particular, targeted antibiotic therapy has been highlighted. [1]. Given the potential seriousness of these infections, it is important to sensitize healthcare professionals to take Vibrio into account in their therapeutic strategy when risk factors are identified (exposure to the marine environment, consumption of seafood).

2.2. JUSTIFICATION OF THE REQUEST FOR DEROGATION FROM INDIVIDUAL INFORMATION

The rarity of cases requires data collection from old records. It is planned to go back as far as 2000. A significant number of patients, who will no longer be followed up in the center where the diagnosis of vibriosis was made, is therefore to be expected. An authorization for a waiver of information is being sought as it will be difficult to locate the patients concerned.

3. OBJECTIVES

3.1. PRIMARY OBJECTIVE

To describe the clinical and epidemiologic characteristics of patients diagnosed with non-cholera Vibrio infection.

3.2. SECONDARY OBJECTIVES

Describe the different clinical forms (gastroenteritis, moderate to severe skin disorders, bacteremia, ear infections) according to the different environmental contexts, particularly meteorological.

4. DESIGN

Data-driven, retrospective, multi-center study

5. ELIGIBILITY CRITERIA

5.1. INCLUSION CRITERIA

Cases of vibriosis, other than Vibrio cholerae O1-O139, diagnosed between January 2000 and November 2019 will be included.

A non-epidemic Vibrio infection is defined by a biological sample (blood culture, superficial sample, deep sample, ear sample) positive to a Vibrio species other than Vibrio cholerae O1-O139 taken from any patient.

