6. EVALUATION CRITERIA

6.1. PRIMARY OUTCOME

Socio-demographic, clinical and therapeutic criteria.

Details about the variables collected:

Non-epidemic Vibrio infections can give four main clinical pictures:

- 1) skin infections ranging from simple dermohypodermatitis to necrotizing fasciitis (skin damage with sores, blisters or necrosis will be sought)
- 2) Digestive infections such as acute gastroenteritis (diarrhea, nausea, vomiting).
- 3) bacteraemia with a more or less severe sepsis pattern (fever, hemodynamic instability, dyspnea). The entry portal can be varied: digestive, cutaneous or pulmonary.
- 4) ENT infections such as chronic otitis media (we will look for ear pain, discharge, deafness).

Finally, Vibrio infections also give other clinical pictures but less common: pneumonia from inhaling contaminated water (typically from drowning), bone infections from an open fracture in contact with contaminated water.

Vibrio infections are more common when the water temperature rises. More infections are expected during the summer months (June to September). It is therefore interesting to collect the month of exposure and infection in order to confirm this hypothesis.

Therapeutic management is essentially based on antibiotic therapy. The literature shows that the initial antibiotic therapy is often not adapted because Vibrio is rarely taken into account in the first diagnoses. It is therefore voluntary to let the antibiotic therapy be specified rather than restricting the choice to a few molecules. Finally, in severe skin infections such as necrotizing fasciitis, surgical treatment such as debridement, lavage or amputation is necessary. Sometimes there is a need for several surgical revisions.

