7.1. SAMPLE SIZE

The study carried out by the National Reference Center for Vibriosis and Cholera between January 1995 and December 1998 reported 29 cases of non-cholera vibriosis infections [5]. More than half (n=16) resided in a coastal department and 7 were from the Atlantic coast.

Vibrios do not develop in waters with a high degree of salinity, which is why they are rarely isolated in France.

Data collection in the hospital centers of Poitiers, La Rochelle, Tours, La Roche-sur-Yon, Nantes, Angers, Rennes and Bordeaux will make it possible to describe almost all Bay of Biscay and Celtic sea cases. Between 50 and 60 cases are thus expected over a period of 19 years in all participating centers.

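### The case definition in section 5.1 does not name stool, so read literally it leaves out stool-proven gastroenteritis, a form the study sets out to describe

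*Combined protocol and SAP*

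**What the plan says.** Section 5.1 has two sentences on who is a case. The opening one is broad: "Cases of vibriosis, other than Vibrio cholerae O1-O139, diagnosed between January 2000 and November 2019 will be included". The next is the operational definition: "A non-epidemic Vibrio infection is defined by a biological sample (blood culture, superficial sample, deep sample, ear sample) positive to a Vibrio species", again other than O1/O139. The bracketed list carries no wording to mark it as examples. The inclusion line of the summary is also broad ("cases of non-epidemic vibriosis"), and section 5.2 excludes only the two epidemic serogroups.

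The forms to be described are wider than the specimen list:

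- Section 2.1, on presentation: "They present themselves in the form of gastroenteritis, severe dermohypodermatitis or necrotizing fasciitis and can lead to septic shock".
- Section 3.2, the secondary objective: "Describe the different clinical forms (gastroenteritis, moderate to severe skin disorders, bacteremia, ear infections", each to be set against environmental and weather conditions.
- Section 6.1, one of four main clinical pictures: "Digestive infections such as acute gastroenteritis (diarrhea, nausea, vomiting".
- Section 6.1, on bacteraemia: "The entry portal can be varied: digestive, cutaneous or pulmonary".

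Section 7.1 gives the expected size without a split by form or specimen: "Between 50 and 60 cases are thus expected over a period of 19 years in all participating centers".

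**The concern.** Stool is the natural specimen for gastroenteritis, and it is the one that the definition does not name. A centre that follows the list would not count a patient with diarrhoea and *Vibrio* in the stool only. Digestive disease would then enter mainly through a positive blood culture, so the digestive group that remains would lean towards invasive illness.

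The study is purely descriptive, and its primary result is the make-up of the series. Selection at entry cannot be corrected later: there is no comparator, no adjustment is planned, and no analysis by specimen type is described. Literal use would understate gastroenteritis and probably seafood exposure, and would overstate bacteraemia and severity. The secondary objective could not be met for stool-only gastroenteritis.

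The broad and narrow sentences of 5.1 also allow two searches of the laboratory records. If some of the eight hospital centres in 7.1 count stool isolates and others do not, part of any difference in case mix between them comes from the rule.

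**Working it through.** **Step 1: compare the forms with the specimens.** The main pictures come from section 6.1 and the specimens from 5.1.

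| Main clinical picture (6.1) | Matching specimen in 5.1 |
|---|---|
| Skin | superficial, deep |
| Digestive | none |
| Bacteraemia | blood culture |
| ENT | ear |

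Three of the four pictures have a specimen of their own; the digestive one does not. This comparison is the whole basis of the finding. The plan states no figure that could be reproduced on this point.

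**Step 2: effect on proportions.** Let N be the number of true cases and s the share with no positive specimen other than stool. The literal rule drops N·s cases and keeps N(1−s). A stool-only case has no positive blood culture, so the number of bacteraemias is unchanged and its proportion is multiplied by 1/(1−s), whatever its true value.

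| s | 1/(1−s) |
|---|---|
| 5% | 1.05 |
| 10% | 1.11 |
| 20% | 1.25 |
| 30% | 1.43 |
| 40% | 1.67 |

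**Step 3: illustrative counts.** The only input from the documents is N = 50 to 60 (7.1), taken here as all cases including stool-only; 55 is the midpoint. Two shares are assumed, with no source in the documents:

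- g, the share of cases with gastroenteritis: 0.20 to 0.40.
- b, the fraction of these that are also blood-culture positive: 0 to 0.20.

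Then s = g(1−b), from 0.20 × 0.80 = 0.16 to 0.40 × 1 = 0.40.

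- Cases lost, N·s: 8.0 to 20.0 at N = 50; 8.8 to 22.0 at N = 55; 9.6 to 24.0 at N = 60.
- Cases kept at N = 55: 46.2 down to 33.0.
- Digestive cases kept, N·g·b: 0 to 60 × 0.40 × 0.20 = 4.8. If stool counts, N·g runs from 50 × 0.20 = 10 to 60 × 0.40 = 24.
- Apparent gastroenteritis share, g·b/(1−s): 0 to 0.08/0.68 = 0.12, against an assumed true 0.20 to 0.40.
- Bacteraemia multiplier: 1/0.84 = 1.19 to 1/0.60 = 1.67.

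**Step 4: if 50 to 60 already leaves out stool-only cases.** The full series is N/(1−s), from 50/0.84 = 59.5 to 60/0.60 = 100. Section 7.1 does not say which reading applies.

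**The case against.** The strongest reply is that the bracketed list was meant as examples. The opening sentence of 5.1 and the summary put no limit on specimens, 5.2 does not exclude stool isolates, and gastroenteritis is an explicit target. Section 6.1 also mentions pneumonia although no respiratory specimen is listed, which fits a loose list. *Superficial* and *deep* are undefined. If stool was always meant to count, the true loss is zero. This reading is possible, but the sentence is worded as a definition, and it names ear samples separately, so stool would be expected to be named too. A list that can be read both ways still has to be corrected before the records are searched.

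The annexes and the case report form are not in the available text and may name specimens or already collect specimen type. That stands as a limit on what can be said about the data items. The definition in 5.1 would still have to agree with them.

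Sections 9.2 and 12.3 place monitoring and data management centrally, and no comparison between centres is planned. This weakens the between-centre point but does not remove it, since section 12.1 speaks of data that the centres supply.

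The shares in the illustration are assumptions, and it counts only blood culture as a second route into the series; other listed specimens would retain a few more cases. The effect on seafood exposure is a probable direction only, because a bacteraemia with a digestive portal would stay in. All of this is accepted, and the finding does not depend on those figures.

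**Conclusion.** The concern holds. As written, the definition in 5.1 omits stool-only gastroenteritis, while 3.2 and 6.1 promise to describe the digestive form. Confidence is high for that mismatch, which rests on the wording alone, and it should be put right before case finding and abstraction.

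The size cannot be derived from the documents. It depends on how the list is applied and on the stool-only share s. Under literal use, with the assumed s of 16% to 40%, between 8 and 24 of 50 to 60 cases would be lost. At most about 5 digestive cases would be left to describe by weather, instead of 10 to 24. The multiplier 1/(1−s) for the bacteraemia proportion holds at any s.

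**What to change.** 1. In 5.1, add *stool culture* to the specimen list, or replace the list with *any clinical specimen*.
2. Include stool results in the laboratory search at every centre.
3. Record specimen type for each case, and show the main results with and without stool-only cases.
4. If stool-only cases are left out on purpose, say so in 5.1. State in 3.2 and 6.1 that the digestive form is limited to cases with another positive listed specimen, and restrict the conclusions to match.
5. In 7.1, state whether the expected 50 to 60 cases include stool-only cases.

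The cost is one line in 5.1, one variable if it is not already collected, and a search of stool results at each centre. Abstraction work rises by s/(1−s) over the literal-rule count: 0.16/0.84 = 19% to 0.40/0.60 = 67% under the same illustrative assumptions. If the 50 to 60 already excludes stool-only cases, the total becomes about 60 to 100.

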5.2. EXCLUSION CRITERIA

Cases of Vibrio cholerae O1 and O139.

6. EVALUATION CRITERIA

6.1. PRIMARY OUTCOME

Socio-demographic, clinical and therapeutic criteria.

Details about the variables collected:

Non-epidemic Vibrio infections can give four main clinical pictures:

- 1) skin infections ranging from simple dermohypodermatitis to necrotizing fasciitis (skin damage with sores, blisters or necrosis will be sought)
- 2) Digestive infections such as acute gastroenteritis (diarrhea, nausea, vomiting).
- 3) bacteraemia with a more or less severe sepsis pattern (fever, hemodynamic instability, dyspnea). The entry portal can be varied: digestive, cutaneous or pulmonary.
- 4) ENT infections such as chronic otitis media (we will look for ear pain, discharge, deafness).

Finally, Vibrio infections also give other clinical pictures but less common: pneumonia from inhaling contaminated water (typically from drowning), bone infections from an open fracture in contact with contaminated water.

Vibrio infections are more common when the water temperature rises. More infections are expected during the summer months (June to September). It is therefore interesting to collect the month of exposure and infection in order to confirm this hypothesis.

Therapeutic management is essentially based on antibiotic therapy. The literature shows that the initial antibiotic therapy is often not adapted because Vibrio is rarely taken into account in the first diagnoses. It is therefore voluntary to let the antibiotic therapy be specified rather than restricting the choice to a few molecules. Finally, in severe skin infections such as necrotizing fasciitis, surgical treatment such as debridement, lavage or amputation is necessary. Sometimes there is a need for several surgical revisions.

7.1. SAMPLE SIZE

The study carried out by the National Reference Center for Vibriosis and Cholera between January 1995 and December 1998 reported 29 cases of non-cholera vibriosis infections [5]. More than half (n=16) resided in a coastal department and 7 were from the Atlantic coast.

Vibrios do not develop in waters with a high degree of salinity, which is why they are rarely isolated in France.

Data collection in the hospital centers of Poitiers, La Rochelle, Tours, La Roche-sur-Yon, Nantes, Angers, Rennes and Bordeaux will make it possible to describe almost all Bay of Biscay and Celtic sea cases. Between 50 and 60 cases are thus expected over a period of 19 years in all participating centers.

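### Does the forecast of 50 to 60 cases in section 7.1 need correcting because the cited Atlantic count scales to only 33 to 35?

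*Combined protocol and SAP*

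**What the plan says.** Section 7.1 (Sample size) starts from a national reference-centre series which "between January 1995 and December 1998 reported 29 cases of non-cholera vibriosis infections". It then locates those cases: "More than half (n=16) resided in a coastal department and 7 were from the Atlantic coast". It names eight participating hospital centres and says that collecting their data "will make it possible to describe almost all Bay of Biscay and Celtic sea cases". The forecast follows at once: "Between 50 and 60 cases are thus expected over a period of 19 years in all participating centers". No rate, multiplier, trend or centre-level count connects the series to the forecast. The summary gives the same range of 50 to 60 patients, and section 7.2 repeats the sentence.

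Two other places bear on the point. Section 5.1 sets the window: cases "diagnosed between January 2000 and November 2019 will be included". Section 2.1 says of ascertainment: "Due to their rarity, Vibrio infections are very little known and therefore probably under-diagnosed". The summary confines the analysis to description: means, standard deviations, medians and percentages.

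**The concern.** The word *thus* presents 50 to 60 as the result of a calculation. The catchment is described as the Bay of Biscay and Celtic Sea, so a reader naturally takes the 7 Atlantic cases as the base and gets 33 to 35. The coastal count and the national count both overshoot the range. The stated period is also shorter than the window in section 5.1, and near-complete coverage seems to sit badly beside probable under-diagnosis.

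This is the protocol's only planning number. If the true yield were nearer 35, percentages would be less precise than expected and the breakdown by clinical form and environmental context would be thinner. The background section raises a possible increase with global warming, so a reader might also mistake an excess over the cited rate for rising incidence.

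**Working it through.** **Inputs**
- Reference period, January 1995 to December 1998: 4 years (7.1).
- Reference counts: 29 in all, 16 coastal, 7 Atlantic (7.1). The remainder outside coastal departments is 29 − 16 = 13.
- Study period: 19 years as stated in 7.1. The window in 5.1, counted from the start of January 2000 to the end of November 2019, is 239 months, and 239/12 = 19.92 years.

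**Attempt to reproduce 50 to 60.** Expected cases = (reference count / 4) × study years.

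| Base | Over 19 years | Over 19.92 years |
|---|---|---|
| 7 Atlantic | 33.3 | 34.9 |
| 16 coastal | 76.0 | 79.7 |
| 29 in all | 137.8 | 144.4 |

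No raw count reproduces the range. From the 7 Atlantic cases the rate is 7/4 = 1.75 per year. The forecast needs 50/19 = 2.63 to 60/19 = 3.16 per year, which is 1.50 to 1.80 times that rate. Over 19.92 years it needs 2.51 to 3.01 per year, or 1.43 to 1.72 times.

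**Is 7 the right base?** Section 7.1 does not say so. The sentence is about where cases lived, and the 7 appear to be a subset of the 16 coastal residents. The study counts patients diagnosed at the eight centres, several of them in inland cities, and section 5.1 sets no residence condition. Some of the 13 other cases therefore belong in the base.
- Adding 4 of the 13: 11/4 × 19 = 52.3 and 11/4 × 19.92 = 54.8.
- Adding 5 of the 13: 12/4 × 19 = 57.0 and 12/4 × 19.92 = 59.8.
- Allocating all 13 by the Atlantic share of coastal cases: 29 × 7/16 = 12.7 per four years, giving 60.3 over 19 years and 63.2 over 19.92.

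The protocol describes none of these routes. They show only that a modest allowance reaches the range.

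**Uncertainty in a count of 7.** The exact Poisson 95% interval is 2.81 to 14.42 events. Multiplied by 19/4 it becomes 13 to 69 cases; multiplied by 19.92/4 it becomes 14 to 72. Both contain 50 to 60. With the rate uncertainty carried through (Jeffreys prior, negative binomial prediction), the chance of at least 50 cases is 16% over 19 years and 19% over 19.92. Fixing the rate at exactly 1.75 per year would cut this to about 1% or less, but seven events cannot support that certainty.

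**The period.** 34.85 − 33.25 = 1.6 cases. This is rounding and neither creates nor closes the gap.

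**Precision.** The worst-case 95% half-width is 1.96 × √(0.25/n): 17.1 points at n = 33, 16.6 at 35, 13.9 at 50 and 12.7 at 60. These values depend on the number of cases found, not the number forecast.

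**Coverage.** In a study of existing records, describing almost all cases is most naturally read as almost all diagnosed cases. That is compatible with many infections never being diagnosed.

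**The case for a change.** The best argument for a change is that a figure presented as derived should be derivable, and this one is not. The stated catchment points to the Atlantic count, which falls about a third short of the forecast. No allowance for non-coastal residents, better detection or trend is written down. A sentence giving the source, and a period matched to section 5.1, would cost nothing.

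Most of that stands as a comment on clarity: the derivation is absent and *thus* claims more than the text supports. It does not stand as an arithmetic error, because 33 to 35 also rests on a choice of base that section 7.1 does not make. Replacing 50 to 60 with 35 would exchange one unverified figure for another.

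The suggested consequences are weak. The protocol has no incidence objective or outcome, so an incidence reading would go beyond anything it plans to report. Nor does the forecast determine the precision of the results.

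**Conclusion.** No change to the plan is needed. The forecast is unexplained, not shown to be wrong: it sits 1.4 to 1.8 times above the simple Atlantic extrapolation, inside the uncertainty of a count of 7, and within reach of a small allowance for non-coastal residents. The period mismatch is rounding worth about 1.6 cases, and the coverage and under-diagnosis statements can both be true.

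The deciding consideration is that the number governs nothing. The study takes in all eligible records in a fixed window, describes them, and has no test, power target, planned interval or stopping number. Whether 35 or 60 cases are found, the same records enter and the same summaries are produced, with the achieved count reported.

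This rests on two readings: that the reference counts refer mainly to residence, and that coverage means diagnosed cases. If 7 were instead the complete Atlantic catchment, the forecast would look optimistic, but inclusion and analysis would still be unchanged.
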